4. COMPLIANCE

5. SEVERE ADVERSE EVENTS

6. STATISTICAL ANALYSIS AND METHODS

7. REPORT AND DATA PUBLICATIONS

1. INTRODUCTION

1.1. Study background and substantiation

Neuromuscular diseases (NMD) — the extensive group of the genetically heterogeneous diseases, main clinical manifestations of which are weakness and atrophies of different groups of muscles. These conditions hold the first place on the prevalence of all genetic diseases of nervous system. Total prevalence of neuromuscular diseases amounts to approximately 1 on 3-3.5 thousand in different populations (Madigan R.R., 1981; Majd M.E., 1997; McCarthy R.E., 1999). National Russian register now includes more than 1200 patients. However, if we distribute this statistics to the whole Russian population, we can expect about 48 000 NMD patients in Russia. Progressive muscular dystrophies and spinal amyotrophies are the most common diseases in this group (13-33 cases per 100'000 and 10 cases per 100'000, respectively (McCarthy R.E., 1999). These groups of diseases manifest themselves always in childhood, at the age of 1-10 years (depending on the nosological entity). The course is aggressive and characterized by spinal deformity aggravation and pelvic shift ([Benson E. R. et al., 1998; Berven S., Bradford D., 2002; Wang C. H. et al., 2007; Chandran S. et al., 2011; Cheuk D.K.L. et al., 2015; Halawi M. J. et al., 2015]).

Due to the pathogenesis of neuromuscular deformity patients with such conditions have inevitable progression of spine and thorax deformity, even patients with the mature skeleton and minimal deviations (up to 20-25° by Cobb) in frontal and/or sagittal plane (Larsson E.L. et al., 2005). Early usage of rigid corset prevents significant progression at the childhood but can cause contact dermatitis and pressure ulcers. In this connection many authors insist on surgical spine stabilization at the second growth spurt (Master D.L., 2011). Patients with such conditions usually have severe and long C-type and S-type deformities with pelvic misalignment in frontal and sagittal planes. With S-type deformity body balance is often compensated, but both curves can reach 100° or more (Lonstein J., 2001). With deformity over 40° patients lose the ability to get to the vertical position and can sit only with the support. With deformity over 90° patients cannot sit (Bridwell K.H. et al., 1999; Berven S., Bradford D., 2002; Wang C.H. et al., 2007; Auerbach J.D. et al.m 2009; [name] et al., 2013). Patients in a wheelchair (III functional class by GMFCS - Gross Motor Function Classification System) have high risks of severe deformities in comparison with the bed-bound patients, due to the constant axial load (Lonstein J., 2001; Teli M. et al., 2005). Frequent reference to cardiopulmonary failure as main diagnosis in autopsy results confirms that decompensated spine deformity is the main reason for premature death of such patients (Pehrsson K., 1992; Berven S., 2002; Larsson E.L. et al., 2005; Sarwark J., 2007; Chong H.S., 2011).

Duchenne muscular dystrophy patients studies showed disease progression in all patients with deformity over 40° associated with difficulties while sitting, decrease in vital capacity, decreased performance and problems with hand movements (Hsu, 1983).

Indications for surgical correction of scoliosis in patients with NMD are progressive deformity, loss of balance while seating, back pain and discomfort (Herring JA., 2002; Labelle H, 2002; Renshaw TS, 2001). Such surgery can be performed using connector systems («growing rods») (McElroy MJ, 2011; Chandran S, 2011). The main outcome of treating scoliosis is the stabilization of respiratory parameters and increase in patient activity level (Daher YH, 1985; Brown JC, 1988; Rodillo E, 1989; Phillips DP, 1989; Bridwell KH, 1999; Larsson EL, 2005).

This study will evaluate short-term and long-term effectiveness and safety of the surgical treatment in different NMD patient groups and to create precise recommendations regarding

CHILDren with neuromuscular diseases – efficacy eVALuation of spinal deformity surgeRY via different pedicle screw fixation systems study
CHIVALRY study

diagnostics, approach to treatment selection and long-term management for such patients on the basis of study data

1.2. Study purpose

The purpose of this study is to evaluate efficacy and safety of spinal deformity surgery via different pedicle screw fixation systems in different groups of children with neuromuscular diseases.

1.3. Study description

This study was sponsored by Federal state budgetary institution “Russian scientific center for traumatology and orthopedics” n.a. acad. G.A. Ilizarov” of the Ministry of Health of Russian Federation. The study will take place at this center.

[figure not shown]
It is expected to enroll 70 patients aged 10-18 years with NMD, all of whom will be subjected to thoracic and lumbar spinal deformity surgery.

Patients will be divided into two groups depending on skeletal maturity. The degree of skeletal maturity will be determined on the basis of an X-ray study of spinal and pelvic bones. The type of surgical correction will depend on the group.

[figure not shown]
2. SYSTEM DESCRIPTION AND INTENDED SCOPE

All patients will be implanted with telescopic connector Medtronic CD Horizon Legacy 4.5 and 5.5 under X-ray control (C-arm), intraoperative spinal deformity surgery safety control (NIM Eclipse, Stealth Station S7) and standard anesthetic support.

First group of patients: local dorsal access. Cranial access: at the level of posterior Th2-5 structures and caudally at the level of L4-S2 vertebrae with exposure of posterior upper spines of iliac wings. Skeletization of vertebrae will be done within transverse processes. Pedicle support points are set bilaterally cranially at each segment level for the space of 3 segments. Caudal support base is formed with pedicle screws in lateral masses of the sacral bone or iliac crests at the level of L5-S1 vertebrae (pic. 1). Control fluorography is performed in two standard planes in order to control screw position. Two “dynamic” rods are formed on the basis of the distance between screw heads allowing 2 cm for distraction; these are two rods connected with a longitudinal connector and bent following the normal sagittal spine profile. After that, channels are formed on both sides under m. erector spinae in the cranial/caudal direction. Pre-bent rods with connectors are placed into the prepared channels. The metal construct is stabilized with internal set screws (pic. 2). If necessary, the construct may be stiffened with crosslinks. Control fluorography is performed in two standard planes in order to control implant position and evaluate correction. The intervention completes with local dorsal spinal fusion with an autobone at the level of base screws. The wound is sewn up in layers tightly.

[figure not shown]

Pic. 1. Pedicle screw positioning: 1 – screw heads.

[figure not shown]

Pic. 2. Thoracic and lumbar spine after a “dynamic” fixation system has been implanted: 1 – rod, 2 – longitudinal connector.

Group two: dorsal access to the posterior column is gained in accordance with the preoperative plan. The access length depends on the instrumentation area. Vertebral skeletization is performed within transverse processes. *Subgroup 1 – pedicle support points are set bilaterally at each segment level. Subgroup 2 – pedicle support points are set bilaterally in every second segment* (pic. 3). Segmented instrumentation of 3 cranial segments to prevent dislocation of metal construct elements at the level of Th2-4 or Th3-5 vertebrae is a special measure. Similar to group I, caudal support base is formed with *pedicle* screws in lateral masses of the sacral bone or iliac crests at the level of L5-S1 vertebrae. Control fluorography is performed after that in two standard planes in order to control screw position. Segmented facetectomy is recommended for additional spine mobilization. Pre-bent rods are placed into support points. Deformity correction is performed by means of a translational maneuver, segmented distraction (concave side) and compression (convex side). The metal construct is stabilized with internal set screws (pic. 4). If necessary, the construct may be stiffened with crosslinks. Control fluorography is performed in two standard planes in order to control implant position and evaluate correction. The intervention completes with dorsal spinal fusion with an autograft along the implants. The postoperative bed is subjected to Redon drain. The drainage is exteriorized to the skin via a separate puncture. The wound is sewn up in layers tightly.

Pic. 3. Screw positioning via pedicles: 1 – screw heads.

Pic. 4. Thoracic and lumbar spine after a fixation system has been implanted: 1 – screw heads, 2 – rod.

3. STUDY PLAN

3.1. Study goals and objectives

1. To estimate effectiveness and safety of surgical treatment for spinal deformities with different pedicle screw fixation (PSF) systems in various pediatric patient groups with neuromuscular diseases
2. Considering patient condition, deformity progression, age, physical, motor, cognitive, functional, static and dynamic status present the following:
 - a) Develop diagnostic algorithm for patients with severe deformities of thoracic and lumbar spine following NMD
 - b) Create surgery planning algorithm: instrumentation area planning, number and location of fixation points planning, grounds for spine mobilization and area of mobilization
 - c) Assess effectiveness of the intraoperative safety control technologies - navigation and monitoring during surgical treatment of spinal deformities in NMD patients (Nim Eclipse, Stealth Station S7)
 - d) Evaluate dynamics in physical, static, dynamic and functional status after surgical treatment using special scales

We assume that the study will result in the following:

- introduction of modern surgical methods of treating children with severe spinal deformities at NMD;

CHILDren with neuromuscular diseases – efficacy eVALuation of spinal deformity surgeRY via different pedicle screw fixation systems study
 CHIVALRY study

- development and simulation of individual methods of surgery and spinal system elements for treating children with severe spinal deformities at NMD.

3.2. Endpoints

The primary endpoint is decrease in spine deformity grade by 1 or more (according to Chaklin classification) with stabilization or improvement in lung parameters in 12 months after the surgery.

Secondary endpoints are as follows:

1. Hospitalization by all causes
2. Improvement in life quality after surgery according to scales (VAS, GMFCS, RLAS, FIM, MACS) in 6 months and 12 months after surgery.

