3.8.8. Unscheduled visits

Unscheduled visits – NMD-induced spinal deformity-related visits not required by the study protocol.

If a patient had an unscheduled follow-up visit, the data obtained during such a visit are recorded separately.

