5. SEVERE ADVERSE EVENTS

Information on all severe adverse events (SAE) will be collected throughout the study.

Severe adverse event (SAE) – a medically unfavorable event (adverse event) resulting in one of the following:

- a) Fatal outcome;
- b) Major aggravation of patient's health due to:
 - 1) a life-threatening disease or injury, or
 - 2) a persistent function impairment or structural damage, or
 - 3) a condition requiring hospitalization or increased duration of inpatient stay;
 - 4) a condition requiring additional therapeutic intervention or surgery to prevent a life-threatening disease or injury.

Information on SAE will be collected throughout the study from the moment of signing the informed consent form. Reports on these effects will be sent to the LEC. These reports will contain the following information:

- Date of the SAE;
- Description of the SAE;
- Treatment of the SAE;
- Outcome;
- Evaluation of severity of the SAE and its connection with the index procedure.

The type and duration of SAE observation will depend on its classification; treatment will be conducted at the investigator's discretion. Patients will be followed up until SAE are resolved, patients withdraw from the study or the study is completed, whichever is the soonest. If a patient withdraws from the protocol before the study is completed, maximum efforts will be made to continue following a patient up until SAE are resolved or deemed persistent without the need in further action.

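### The primary endpoint gives no consequence to unplanned re-operation before month 12, so a patient whose construct was revised can be counted as a success of it or left out

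*Combined protocol and SAP*

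**What the plan says.** - **Endpoint.** Section 3.2 has two components, deformity and lung function: "decrease in spine deformity grade by 1 or more (according to Chaklin classification) with stabilization or improvement in lung parameters". The time point is 12 months after surgery. Revision, implant removal and change of system are not mentioned.
- **Month-12 assessment.** Table 1 and Section 3.8.7 schedule the Visit 6 X-ray for every patient, with no condition on intervening surgery. Spirometry at that visit is optional.
- **Where a re-operation would be recorded.** If it needs admission, it falls under the first secondary endpoint, "Hospitalization by all causes", and under item b)3 of the SAE definition in Section 5. Item b)4, "a condition requiring additional therapeutic intervention or surgery to prevent a life-threatening disease or injury", covers some cases too, but a broken rod need not threaten life. For unscheduled deformity-related visits, Section 3.8.8 says that "the data obtained during such a visit are recorded separately". None of these records is linked to the primary endpoint.
- **Withdrawal and missing data.** Section 3.8.9 does not list re-operation by name, but the investigator may withdraw a patient on medical grounds, and collection then stops. Section 6 marks missing values N/A and leaves them out of the summaries.
- **Distraction.** Section 2 says the group 1 rods are "formed on the basis of the distance between screw heads allowing 2 cm for distraction". No later distraction is scheduled anywhere.

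**The concern.** Section 3.1 sets out to estimate effectiveness and safety of surgery with different pedicle screw systems. A construct that fails and has to be revised within a year is about the least favourable result a system can have, yet the primary endpoint does not register it. Construct failure is also foreseeable from the protocol itself: Section 2 describes segmental instrumentation of three cranial levels in group 2 specifically to keep the construct from dislocating.

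The gap matters most when results are set side by side by group, and Section 6 does plan tests of differences between groups. If revision is more frequent with one system, the endpoint as written can hide that. In an open, single-center study, choosing case by case between keeping a revised patient to month 12 and withdrawing that patient also brings discretion into the primary result.

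**Working it through.** **1. Inputs.** Section 1.3: "It is expected to enroll 70 patients aged 10-18 years with NMD". Section 3.3: 30 in group 1 and 40 in group 2; 30 + 40 = 70, so the totals agree. Subgroup sizes are not stated. No revision rate, expected success rate or power is given, so the plan has no other figure to reproduce.

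**2. Possible routes for a patient revised at, say, month 8.**

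| Route | Basis | Effect on the success rate |
|---|---|---|
| Stays in; month-12 grade and lung parameters qualify | 3.2, 3.8.7 | Success of the index fixation group |
| Stays in; either component fails | 3.2 | Failure |
| Stays in; no month-12 spirometry | Table 1, 3.8.7, 6 | Lung component unknown; may be N/A |
| Withdrawn on medical grounds | 3.8.9, 6 | N/A, out of the denominator |

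Only the second route records a failure, and then not because of the revision.

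**3. Weight of one patient.** Moving one revised patient from success to failure lowers the rate by 100/n points: 100/30 = 3.3 in group 1, 100/40 = 2.5 in group 2, 100/70 = 1.4 overall.

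**4. First route, overall size.** Overstatement = r × s, where r is the share re-operated and s the share of those who meet the whole endpoint, lung component included. Assumed: r = 5% to 20%, s = 80%.

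- r = 5%: 70 × 0.05 × 0.8 = 2.8 patients; 2.8/70 = 4.0 points
- r = 10%: 70 × 0.10 × 0.8 = 5.6 patients; 5.6/70 = 8.0 points
- r = 20%: 70 × 0.20 × 0.8 = 11.2 patients; 11.2/70 = 16.0 points

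**5. Withdrawal route.** Illustration with an assumed apparent success rate of 80%, in which every revised patient would otherwise have met the endpoint (s = 100%, so these figures are not directly comparable with step 4).

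| Group | Revised | Counted as success | Scored as failure | Dropped as N/A |
|---|---|---|---|---|
| 1 | 2 | 24/30 = 80% | 22/30 = 73% | 22/28 = 79% |
| 1 | 3 | 24/30 = 80% | 21/30 = 70% | 21/27 = 78% |
| 1 | 6 | 24/30 = 80% | 18/30 = 60% | 18/24 = 75% |
| 2 | 2 | 32/40 = 80% | 30/40 = 75% | 30/38 = 79% |
| 2 | 4 | 32/40 = 80% | 28/40 = 70% | 28/36 = 78% |
| 2 | 8 | 32/40 = 80% | 24/40 = 60% | 24/32 = 75% |

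Dropping revised patients recovers only a small part of the gap. It still exceeds the revision-free rate by about 4 points (group 2, 2 revised: 78.9 − 75.0) to 15 points (6 revised in group 1 or 8 in group 2: 75 − 60).

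**The case against.** The strongest reply is that scoring the month-12 state whatever happened in between is a legitimate treatment-policy choice. Section 3.1 speaks of surgical treatment with these systems, not of the implants alone, and Section 3.3 calls the study non-comparative. On that view, a child revised at month 8 who is better at month 12 has been treated successfully. This stands as an argument for keeping that rate in the report. It does not show that the choice was made: nothing in Sections 3.2 or 6 states it, and the withdrawal route contradicts it, since a treatment-policy rate needs month-12 data on revised patients.

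It can also be said that re-operations are not lost, because admissions count under a secondary endpoint and as SAEs. That is correct, but all-cause hospitalization is not specific to the device, and neither record changes the primary result.

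Third, sampling error is already wide: 24/30 has an exact 95% interval of 61% to 92%. That is true, but the interval does not allow for a shift caused by the scoring rule.

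Finally, the size rests on assumed rates. This is conceded in full.

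**Conclusion.** The gap is real and worth closing, at modest cost. The primary endpoint gives no consequence to unplanned revision, removal or change of system before month 12. A revised patient can therefore be a success of the index construct or drop out of the denominator, and both tend to raise the stated rate relative to revision-free success. The shift per reclassified patient (3.3, 2.5 and 1.4 points) follows from the planned group sizes. The range of 4 to 16 points overall rests on the assumed 5% to 20% re-operated and 80% meeting both components.

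Three stronger readings are tempting and are not supported:

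- **That the plan rules a revised patient a success.** It is silent; success is one possible outcome. The lung component must also be met, so the film alone does not decide.
- **That re-operation appears only as an SAE.** An admission for it also counts under the first secondary endpoint.
- **That later distraction makes the group 1 film a different kind of measurement.** The rods are built with a distraction allowance, but no later distraction is documented. Distraction belongs to that system's design and is not construct failure.

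**What to change.** In Section 3.2:

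1. State that month 12 runs from the index surgery.
2. Define success as the present two criteria without unplanned re-operation on the instrumented spine (revision, removal or change of system) before Visit 6. Patients with such a re-operation are non-responders, even if later withdrawn.
3. State that planned distraction in group 1, if it occurs, is not a failure; record its date.

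In Section 6:

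4. Report this rate by group and subgroup beside the rate as now defined, labelled as the treatment-policy version.
5. Report the number of revisions by group.
6. Show how many patients lack the lung component, by revision status. Revised patients would always be classifiable, whereas unrevised patients without spirometry would not, and the reader needs to see that imbalance.

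The cost is a few sentences, a date field for distraction and one extra table. Section 5 already requires the date, description and treatment of each SAE, which should identify revisions that need admission. The downside is a somewhat lower stated success rate. Only the scoring changes; clinical management does not.

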3.3. Study design

This study is prospective, non-randomized, single-center, open and non-comparative; it involves two parallel groups of patients (children aged 10-18 years) with severe thoracic and lumbar spinal deformities at NMD.

Patients are divided into groups depending on skeletal maturity determined on the basis of an X-ray study of spinal and pelvic bones. The type of surgical correction will depend on the group.

1. Group of patients with spinal deformities corrected and stabilized with bilateral connector systems (growing skeleton).

Bone maturity grades I-III (Sadofyeva classification) or I-II (Risser classification).

Bilateral connector systems (“growing rods”) will be used in this group (N = 30).

2. Group of patients with spinal deformities corrected and stabilized with bilateral multiple fixation points (mature skeleton).

Bone maturity grades IV-V (Sadofyeva classification) or III-IV (Risser classification).

Inside this group (N=40) two subgroups are planned depending on varying anatomic characteristics thus allowing for specific treatment option:

- *Subgroup 1 – segmental fixation*
- *Subgroup 2 – intermittent (next nearest) segment fixation*

Patients will be enrolled in study groups in consecutive stages, according to enrollment criteria described above

3.4. Patient population

The targeted population of this study includes underage patients of both male and female aged 6-25 years with neuromuscular diseases (spinal atrophies, myopathies, myodystrophies).

3.5. Study duration

The follow-up period for each patient will be at least 12 months. Enrollment of patients will continue for 24 months. The expected total study duration is 36 months (12 months after enrollment of the last patient).

3.6. Inclusion/exclusion criteria

A patient should meet the inclusion criteria and lack all exclusion criteria to be considered.

Inclusion criteria:

1. Signed and dated informed consent for participation in the study (separate informed consents for child and parents/caregivers), obtained before conducting any study procedures
2. Age from 6 to 25 years

CHILDren with neuromuscular diseases – efficacy eVALuation of spinal deformity surgeRY via different pedicle screw fixation systems study
CHIVALRY study

3. Male and female patients
4. Verified and documented diagnosis with the results of neurologic examination
5. Deformity of thoracic and/or lumbar spine associated with NMD, which requires surgical intervention

Exclusion criteria:

1. Patient unwillingness or inability to follow study procedures
2. Absence of signed and dated informed consent for participation in the study (as for child and for parents/caregivers)
3. Patient participation in another clinical study, which can influence the results of this study
4. Life expectancy <12 months
5. Concomitant diseases, which preclude patient participation in this study according to doctor's opinion

Participant exclusion criteria:

Patients may be excluded from the study at any time. The reasons for exclusion may be as follows:

1. Voluntary patient withdrawal (consent withdrawal for any reason or without giving a reason) without negative effects on further treatment.
2. Failure to follow-up a patient.

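### Sections 1.3 and 3.3 describe patients aged 10-18, but section 3.4 and inclusion criterion 2 admit ages 6 to 25, and nothing reconciles the two ranges

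*Combined protocol and SAP*

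**What the plan says.** The age of the study population is given four times in the combined protocol and SAP.

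- Section 1.3 (study description): "It is expected to enroll 70 patients aged 10-18 years with NMD".
- Section 3.3 (study design): "two parallel groups of patients (children aged 10-18 years", in a parenthesis within the design statement.
- Section 3.4 (patient population): "underage patients of both male and female aged 6-25 years".
- Section 3.6, inclusion criterion 2: "Age from 6 to 25 years".

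Section 3.6 makes its criteria the condition for entry: "A patient should meet the inclusion criteria and lack all exclusion criteria to be considered". The purpose in 1.2 is to evaluate surgery "in different groups of children with neuromuscular diseases", and objective 1 in 3.1 is set "in various pediatric patient groups with neuromuscular diseases".

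The consent text assumes a minor. Inclusion criterion 1 asks for "separate informed consents for child and parents/caregivers", and exclusion criterion 2 bars a patient for whom these are absent. Sections 3.8, 3.8.1 and 3.8.2 ask for signatures from the patient and the parents; 3.8.1 accepts one parent.

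**The concern.** Age is a basic eligibility rule. It decides who undergoes the study procedures and whom the conclusion describes. Here the numbered criterion and the design description disagree at both ends of the range. Someone who screens by criterion 2 may accept a 7-year-old or a 22-year-old, and someone who works from 3.3 may not. A monitor, an ethics committee or a later reader cannot tell from the text which of them followed the plan.

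The population label is affected too. The title, purpose and first objective speak of children or pediatric groups, whereas criterion 2 reaches age 25. If adults are enrolled, a conclusion stated for children would not describe everyone analysed.

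A secondary question follows for consent. The age criterion may admit adults, but the text gives no way for an adult to enter without a second signature from a parent or caregiver.

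**Working it through.** The plan has no calculated figure to reproduce here. The check compares the passages and counts whole-year ages.

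**Step 1. The ranges side by side**

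| Section | Age range | Label used | Role of the text |
|---|---|---|---|
| 1.3 | 10-18 | none with the range | expectation for enrolment |
| 3.3 | 10-18 | children | design description |
| 3.4 | 6-25 | underage | target population |
| 3.6, criterion 2 | 6-25 | none | numbered entry criterion |

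The text available for review contains no amendment history or cross-reference that would explain the difference. The word underage stands in 3.4 only.

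**Step 2. Size of the mismatch in single-year ages**

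- Admitted by criterion 2: 25 − 6 + 1 = 20.
- Covered by 3.3: 18 − 10 + 1 = 9.
- Admitted but not covered: 20 − 9 = 11, made up of 4 below (6-9) and 7 above (19-25).

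**Step 3. Is the label underage compatible with 6-25?** The documents state no age of majority, so it has to be assumed.

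- Majority at 18: adult ages admitted = 25 − 18 + 1 = 8 (18-25).
- Majority at 21: adult ages admitted = 25 − 21 + 1 = 5 (21-25).

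Under either assumption 3.4 conflicts with its own label. With majority at 18, one adult age (18) also lies inside 10-18.

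**Step 4. What the conflict leaves alone.** Section 3.3 assigns patients to groups, and so to a type of surgery, by bone maturity grade (Sadofyeva or Risser), not by age. The group sizes add to the stated total, 30 + 40 = 70, whichever age range applies.

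**Step 5. Consent.** The patient's own signature is required throughout. Section 3.6 asks in addition for parents or caregivers; 3.8, 3.8.1 and 3.8.2 name parents only. An adult with a parent who signs can satisfy all of these. An adult with neither a parent nor a caregiver to sign meets criterion 2 but falls under exclusion criterion 2.

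**The case against.** The strongest reply is that criterion 2 is the only numbered age rule, that 3.4 agrees with it, and that 10-18 is merely descriptive: a forecast in 1.3 and a parenthesis in 3.3. Much of this stands. A reader might infer that 3.3 excludes ages 6-9 and 19-25, but it is not worded as an exclusion. Its closing sentence does refer to enrolment criteria set out above it. That may mean only the maturity grades, or it may take in 10-18 as well, so it makes the text ambiguous and no more. The reply does not remove the contradiction. If criterion 2 governs, 1.3, 3.3 and the label in 3.4 need correcting; if 10-18 governs, 3.4 and criterion 2 do.

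A reader might also take 11 of 20 ages as the share of patients affected. The documents do not support that. They give no age distribution, and a patient must also fit one of the bone maturity grades in 3.3, which are not mapped to ages.

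Finally, a reader might infer that adults could be enrolled without valid consent. The text does not show this, because every patient must sign. What is missing is a route without the second signature, which is an added safeguard or a restriction on recruitment. Section 4 also commits the study to current Russian legislation, ethics committee requirements and the Declaration of Helsinki. That general commitment does not repair the specific wording, but it weakens any claim of improper consent. The consent forms themselves were not available, so only the protocol wording can be judged.

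**Conclusion.** The contradiction is real and stands in current text, in an eligibility rule and not in background prose. Following criterion 2 as written can enrol patients aged 6-9 or 19-25 who do not match the design description; any adults among those enrolled would also lie outside the purpose and objective for children.

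The mismatch is 11 of the 20 single-year ages admitted. The number of patients concerned is unknown and may be zero. No effect on the primary endpoint is claimed, and none on allocation or sample size.

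The consent point is secondary and conditional. It rests on an age of majority that the documents do not give and, apart from age 18 (if majority is 18), on which range is kept. The documents do not settle which range was intended.

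**What to change.** 1. Put one identical age range in 1.3, 3.3, 3.4 and inclusion criterion 2. Which range is for the sponsor and the investigator to decide.
2. If adults remain eligible, correct the words underage and children wherever they describe the population.
3. Keep every patient enrolled under the criterion in force in the analysis, report the enrolled age distribution, and state the conclusion for that population.
4. If adults remain eligible, amend inclusion criterion 1, exclusion criterion 2, 3.8, 3.8.1 and 3.8.2 to say how an adult may consent without a parent's or caregiver's signature. If majority is 18, check this for age 18 under either range. Under 3.8.1, any changed form goes back to the local ethics committee.

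The cost is a short amendment with ethics committee review, plus one line of reporting on ages. The downside is a broader population label if the wider range is kept, or a smaller recruitment pool if the narrower one is.
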